1 PROTOCOL AMENDMENT SUMMARY

This section provides a summary of major changes made to the protocol for Study SN-SIAL-351 in this current amendment (No. 01). Section 25 provides a detailed accounting of all amendment changes.

- Protocol was revised by changing applicable inclusion/exclusion criteria to allow enrollment of subjects who have had prior botulinum toxin A or B injections to the salivary glands, provided that last administration was at least 24 weeks before screening, and previous botulinum toxin A or B exposure to other anatomical locations provided that last administration was at least 12 weeks before screening. Further, enrollment of subjects who previously received botulinum toxin injections would require that prior toxin exposure was well tolerated and without any significant long-term side effects, and subjects, in the Investigator's opinion, must not have failed to respond to previous treatment with botulinum toxin. This change was implemented in order to improve enrollment and to facilitate the collection safety data on subjects who would be likely candidates for treatment with MYOBLOC for sialorrhea in clinical practice.
- Revised exclusion criteria to remove specific exclusion of subjects with moderate to severe dysphagia and moderate to severe choking, and have revised exclusion criteria related to risk of aspiration (moderate to high risk of aspiration is exclusionary). Specific considerations have been provided which should be taken into account when the Investigator determines the subject's level of risk of aspiration. Moderate to high risk of aspiration is defined by any one of the following
 - History of aspiration pneumonia in the last 6 months before screening
 - Speech pathologist and/or formal swallowing test (e.g., with barium, endoscopy, dynamic swallowing study, imaging study, fiber-optic endoscopic swallowing evaluation or other imaging scan) that concludes that a moderate to severe risk of aspiration exists
 - Due to perceived risk of aspiration, a health care professional has recommended PEG or G-tube but subject declined
 - In the investigator's clinical judgment, the subject is at moderate to high risk of aspiration

Subjects whose risk of aspiration are judged by the investigator to be satisfactorily controlled by placement of PEG or G-tube for nutritional support are eligible to participate. Specific criteria excluding subjects with moderate to severe dysphagia or choking within the last 6 months prior to screening have been removed, and instead the protocol focuses solely on the risk of aspiration, taking into consideration that those with a PEG or G-tube (in whom placement of either would mitigate the risk of aspiration associated with a moderate to severe risk dysphagia or choking) may participate. The previous exclusion criteria could be considered too vague or restrictive as it focused on a symptom (dysphagia or difficulty with swallowing) that is common to many neurological disorders and especially frequent in ALS. The

revised inclusion/exclusion criteria now focus on the baseline risk of aspiration because it is aspiration that can lead to significant morbidity and even mortality.

- The requirement to administer the Visual Analog Scale (VAS) to subjects in order to rate severity for dysphagia and dry mouth at every clinic visit has been removed. Administering the scale at every visit, regardless of a reported event of dysphagia or dry mouth, is unnecessary and would result in an overreporting of events. Adverse events of dysphagia and dry mouth will continue to be collected based on subject report and severity will be determined by the Investigator.

Study drug injections should not be administered if an adverse event of dysphagia or dry mouth of moderate to severe severity persists without prior consultation with the Medical Monitor. If the adverse event has not resolved or has not improved to a mild severity by the end of the per protocol window for injections to occur (every 13 ± 2 weeks), the Medical Monitor should be contacted to discuss whether or not the subject should be dosed, discontinued, etc.

- Administrative updates have been incorporated, including a change in the Medical Monitor information.

4 SYNOPSIS

Title	A Phase 3, Long-Term, Open-Label and Single-Arm Study of MYOBLOC [®] in the Treatment of Troublesome Sialorrhea in Adult Subjects
Objectives	
Primary
 
 To determine the long-term safety and tolerability of MYOBLOC (administered intraglandularly as a single total dose of 3,500 Units) treatments every 13 weeks over a maximum possible duration of 1 year in adult subjects with troublesome sialorrhea. 
Secondary
 
 To assess the magnitude of therapeutic response of MYOBLOC (administered intraglandularly as a single total dose of 3,500 Units) using effectiveness assessments performed at intervals after treatments every 13 weeks over a maximum possible duration of 1 year.
Study Design	
Multicenter, open-label, outpatient study of the safety and effectiveness of repeated doses (3,500 Units every 13 weeks) of MYOBLOC over a 1-year duration in adult subjects with troublesome sialorrhea. The study population will be comprised of a mixture of patient populations including, but not limited to, subjects with Parkinson's Disease (PD)-related sialorrhea, sialorrhea secondary to other non-PD conditions (e.g., adult cerebral palsy, amyotrophic lateral sclerosis [ALS], stroke, traumatic brain injury), or sialorrhea secondary to oral cancer or medications (e.g., neuroleptics).
 
All MYOBLOC injections will be performed by Investigators who have prior experience or have been appropriately trained with injecting botulinum toxin. Injections will be guided by external anatomical landmarks or by external anatomical landmarks with ultrasound-guided confirmation. Sites designated as "ultrasound" sites will perform all their injections with ultrasound-guidance.
 
After a screening period (up to 21 days), those subjects who satisfy all eligibility criteria may receive single dose injections of 3,500 Units of MYOBLOC every 13 weeks (± 2 weeks) for a total of 4 treatments via injections into the submandibular and parotid glands. Repeat injections at each treatment session will be done when subjects return to baseline status as determined by the Investigator, with a minimum interval of 11 weeks from the prior injection. If after the first treatment of 3,500 Units the subject develops intolerable side effects, but still wishes to remain in the study, the Investigator has the discretion to decrease subsequent doses, but to no less than a total dose of 2,500 Units.

Study Design (continued)	Subjects will undergo safety and effectiveness assessments at Weeks 4, 8, 13, 17, 26, 30, 39, 43, and 52 as detailed below, and telephone follow up will occur at Weeks 21, 34, and 47.
Sites	20 or more (Target: up to 1 subject/site/month. Recruitment time: 6 to 12 months)
Inclusion Criteria	
 1. Able to read and provide written informed consent before enrollment into the study, or the subject's caregiver (Legally Authorized Representative) can provide written informed consent. 2. Male or female, 18 to 85 years of age (inclusive). 3. Seeking treatment for troublesome sialorrhea for at least 3 months that is occurring secondary to any disorder or related to any cause, including, but not limited to, Parkinson's Disease (PD), adult cerebral palsy, amyotrophic lateral sclerosis (ALS), stroke, traumatic brain injury, oral cancer, and side effects of other medications. Note: A diagnosis of Parkinson's Disease fulfills the UK Parkinson's Disease Society Brain Bank diagnostic criteria. A diagnosis of ALS fulfills the El Escorial World Federation of Neurology criteria. 4. Minimum unstimulated salivary flow rate of 0.2 g/min at screening (unstimulated normal rate is 0.3 g/min) [Wang 1998]. 5. Minimum Investigator's Drooling Frequency and Severity Scale (DFSS) score of 4 (range 2-9, a score of 2 = "never drools") at screening. 6. Ability and availability to participate in the study for up to 1 year (ALS subjects: ability and availability to participate in the study for at least 6 months), based on overall health of the subject and disease prognosis, as applicable, in the opinion of the Investigator, and able to comply with all requirements of the protocol, including completion of study questionnaires. A caregiver may be designated to assist with assessments.
Exclusion Criteria	
 1. A moderate to high risk of aspiration will exclude participation in this study. Moderate to high risk of aspiration is defined by any one of the following: 
 • History of aspiration pneumonia in the last 6 months before screening • Speech pathologist and/or formal swallowing test (e.g., with barium, endoscopy, dynamic swallowing study, imaging study, fiber-optic endoscopic swallowing evaluation or other imaging scan) that concludes that a moderate to severe risk of aspiration exists • Due to perceived risk of aspiration, a health care professional has recommended PEG or G-tube but subject declined • In the Investigator's clinical judgment, the subject is at moderate to

	
high risk of aspiration.
 
Subjects whose risk of aspiration are judged by the Investigator to be satisfactorily controlled by placement of PEG tube or G-tube for nutritional support are eligible to participate.
 
 2. Respiratory forced vital capacity (FVC) of <20% of predicted. FVC will be tested in all ALS subjects, and also in other subjects at Investigator discretion if warranted. 3. Prior botulinum toxin type A or B treatment in the salivary gland(s) identified for treatment in this study within 24 weeks before screening. Prior botulinum toxin type A or B treatment into other anatomical regions not selected for treatment in this study is not exclusionary, but must have occurred at least 12 weeks before screening. 
 • In the Investigator’s assessment, prior toxin exposure must have been well tolerated and without any significant long-term side effects in the case of repeated prior exposure. Subjects should be excluded if, in the Investigator’s opinion, the subject failed to respond to previous treatment with botulinum toxin. Subjects should not receive nor have any plans for receiving any botulinum toxin treatment, other than the study drug (MYOBLOC), during the entire course of the study (from the point the informed consent is signed until subject’s participation is complete). 4. Prior salivary gland surgery. 5. Concomitant use, or exposure within 5 half-lives of screening, of aminoglycoside antibiotics, curare-like agents, or other agents that interfere with neuromuscular function.

Exclusion Criteria (continued)
	
 6. Current treatment or treatment at any time during the study with Coumadin[®] (warfarin) or similar anti-coagulant medications. Anti-platelet medications are not specifically exclusionary. 7. Anticipated or scheduled surgery during the study period. A PEG tube/G tube may be placed for nutritional support at any time during the study and will not exclude the subject from continued study participation. 8. Major surgery (requiring general anesthesia, except PEG tube/G tube placement) within the previous 6 months before screening. If surgery occurred more recently than 6 months before screening, Investigator must have sufficient documentation to demonstrate the subject has fully recovered and stabilized. Prior movement disorder-related surgery (e.g., pallidotomy, thalamic/subthalamic/pallidal deep brain stimulation) will not exclude the subject, provided the surgery was performed at least 6 months before screening. 9. Anticholinergic and antihistamine medication eligibility restrictions: 
 • Oral/transdermal pharmacologic treatment (specifically

	
antihistamines and those medications with anticholinergic properties) for troublesome sialorrhea must be discontinued during the 30-day period before screening and are not allowed in the entire duration of the study, except ALS subjects as allowed herein. For ALS subjects only: such medications for the treatment of sialorrhea are allowed; however, conversion to, or continuation of, a short-acting medication (duration of action of approximately 8 hours or less) is required at a stable dose/regimen at least 2 weeks before the first injection of study drug (i.e., Day 1 of Treatment Session 1). The short-acting anti-cholinergic medication for the treatment of sialorrhea may be continued throughout screening and study participation provided that the ALS subject agrees to hold the medication for at least 8 hours before the screening, baseline, and all subsequent study visits, so that the effectiveness and safety of the study drug can be properly evaluated.
 
 • Antihistamines and anticholinergic medications taken for a non-sialorrhea condition should be avoided as much as possible, but are not exclusionary.

Exclusion Criteria (continued)
	
10. Evidence of any clinically significant neurologic disease (e.g., myasthenia gravis, Lambert-Eaton syndrome), cardiovascular, hematologic (including bleeding diathesis), hepatic, renal, gastrointestinal, endocrine, pulmonary, musculoskeletal, psychiatric disease or condition, or dental condition, which in the judgment of the Investigator or screening dentist would put the subject at risk while in the study, could influence the results of the study, or negatively impact the subject’s ability to participate in the study
 
11. Pregnancy or lactation
 
 • As assessed by the Investigator, females of childbearing potential must agree to practice a medically acceptable method of contraception (e.g., intrauterine device, hormonal contraception started at least one full cycle before study enrollment or barrier method in conjunction with spermicide) for the duration of the study (including 2 months after study completion). For the purposes of this study, all females are considered to be of childbearing potential unless they are confirmed by the Investigator to be post-menopausal (at least 1 year since last menses), biologically sterile, or surgically sterile (e.g., s/p hysterectomy, bilateral oophorectomy, tubal ligation). 
12. History of drug or alcohol abuse currently or within the previous 6 months, as determined by the Investigator.
 
13. Current infection at the sialorrhea treatment injection site(s).
 
14. Participation in another clinical drug, device, or biological agent study

	
within 30 days of screening or while participating in this study.
 
15. Any other condition or clinical finding that, in the opinion of the Investigator and/or the Sponsor, is determined to be unsuitable for enrollment into this study.

Number of Subjects	Approximately 120 to 200 subjects or until requirements of safety database are met.
Safety Endpoints	
 • Occurrence, seriousness, severity, and causality assessment of adverse events at each study visit; • Occurrence of adverse events of special interest (i.e., aspiration, aspiration pneumonia, choking, dysphagia) at each study visit as assessed by the Investigator; • Columbia Suicide Severity Rating Scale (C-SSRS) at each study visit; and • Occurrence of dental adverse events.
Effectiveness Endpoints	
 • Unstimulated salivary flow rate (USFR) (Assessor) at each study visit; • Clinical Global Impression of Severity (CGI-S) and Change (CGI-C) (Assessor) at each study visit; • DFSS-I (Assessor) at each study visit; • DFSS-S as assessed via subject's diary at each assessment time point; • Patient Global Impression of Severity (PGI-S) and Change (PGI-S) at each study visit; and • Drooling Impact Score (DIS) (Subject) at each study visit.
Duration	
The planned duration of participation for each subject is a minimum of 26 weeks and a maximum of 52 weeks (excluding up to a 21-day screening period), including:
 
 • Up to four 13-week (± 2 weeks) treatment sessions over a 1-year period. Note that Treatment Sessions 3 and 4 are likely, but may not be necessary as the study progresses because the study may be stopped early once enough subjects have completed the study to meet FDA safety database requirements. Any subject that enters the study, however, is required to participate at least through 6 months (i.e., complete Treatment Sessions 1 and 2).
Study Visits	
Screening Period: up to 21 days
 
Treatment Session 1
 
Day 1 (day of injection of study drug) and 4 weeks (± 3 days), 8 weeks (± 3 days), and 13 weeks (± 2 weeks) post-injection, and a telephone follow up 24 hours (± 1 day) post-injection.
 
Treatment Sessions 2, 3, and 4
 
For each 13-week treatment session:

	
 • 4 weeks (± 5 days) and 13 weeks (± 2 weeks) after each treatment, with a telephone follow up 1 week (± 1 day) and 8 weeks (± 5 days) after each treatment. Note that the last visit of a prior treatment session will serve as the first day of the next treatment session.
Safety Assessments	
The following safety assessments will be performed as follows:
 
 • Occurrence, seriousness, severity, and causality assessment of adverse events at each study visit or, if applicable, at discontinuation from the study; • Occurrence of adverse events of special interest (i.e., aspiration, aspiration pneumonia, choking, dysphagia) at each study visit or, if applicable, at discontinuation from the study; • Occurrence of dental-related adverse events; • Vital signs at each study visit or, if applicable, at discontinuation from the study; • Complete physical exam at Weeks 4, 13, 26, 39, and 52 (brief at other study visits) or, if applicable, at discontinuation from the study; • FVC in all ALS subjects, and in other subjects if warranted at the discretion of the Investigator, at screening, before the first injection of study drug on Day 1, and at Weeks 4, 8 (as clinically warranted), and 13. Thereafter, FVC will be checked as clinically warranted. • Clinical laboratory safety tests (fasting) at screening and Weeks 13, 26, and 52 or, if applicable, at discontinuation from the study. Laboratory testing will also be done as clinically warranted throughout the study. • Neurologic exam at screening, Day 1 (before first injection of study drug), and Weeks 13 and 52 or, if applicable, at discontinuation from the study. Additional neurologic exams will be performed as clinically warranted. • Dental exam by a licensed dentist at screening and Weeks 4, 13, 26, and 52 or, if applicable, at discontinuation from the study. Four bite-wing radiographs or panoramic imaging (if edentulous or if bite-wing x-rays are difficult due to limited teeth) will be obtained at screening and Weeks 26 and 52 or, if applicable, at discontinuation from the study. Additional dental exams will be performed as clinically warranted based on predefined safety criteria (e.g., persistent severe dry mouth). • Oral exam by the Investigator at each study visit where a dental exam is not required. • Columbia Suicide Severity Rating Scale (C-SSRS) on Day 1 (before first injection of study drug) and each subsequent study visit or, if applicable, at discontinuation from the study.
Effectiveness Assessments	
The following effectiveness assessments will be performed at each study

	
visit:
 
• USFR (Assessor);• CGI-S and CGI-C (Assessor);• DFSS-I;• PGI-S and PGI-C (Subject); and• DIS (Subject). 
In addition, DFSS will be assessed daily via the subject's diary the first 2 weeks after each injection, then weekly for the remainder of each treatment session.

--	---

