Telephone Follow-up					X (o)		X	

Abbreviations: AE = adverse event, BP = blood pressure, C-SSRS = Columbia Suicide Severity Rating Scale, DFSS = Drooling Frequency and Severity Scale, HIPAA = Health Insurance Portability and Accountability Act, RR = respiration rate, Temp = temperature, USFR = unstimulated salivary flow rate, VAS = visual analog scale, wks = weeks

- (a) All screening and baseline assessments and results must be available before injection of MYOBLOC.
- (b) Telephone follow-up.
- (c) Office visit.
- (d) Office visit. Serves as last visit of current treatment session and first visit of subsequent treatment session. Study drug injection will occur after the 13-week assessments have been completed for the prior treatment session.
- (e) Must be obtained before conducting any study procedure.
- (f) Includes baseline history of aspiration, aspiration pneumonia, choking, and dysphagia.
- (g) Includes 4 bite-wing radiographs or panoramic imaging (if edentulous or if bite-wing x-rays are difficult due to limited teeth). If the subject has no teeth, then the dentist will determine if panoramic imaging is required at any visit after screening.
- (h) Females of childbearing potential only.
- (i) Forced vital capacity will be measured in all subjects with amyotrophic lateral sclerosis and in other subjects if warranted at the discretion of the Investigator.
- (j) When possible, assessments should be done by the same person in a given subject to ensure consistency throughout the study.
- (k) Global measure of effectiveness must be completed before USFR.
- (l) Subject-rated via entry in diary (not during study visit), daily for first 2 weeks after study drug injection and then weekly for remainder of treatment session.
- (m) Subjects will receive injections guided by external anatomical landmarks or by external anatomical landmarks with ultrasound-guided confirmation. Sites designated as “ultrasound” sites will perform all their injections with ultrasound-guidance.
- (n) Subjects will be injected after completion of all assessments and then will be contacted by telephone 24 hours (±1 day) post-injection to inquire about their health status and remind the subject to complete their diary.

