15 EFFECTIVENESS ASSESSMENTS

Global Measures of Effectiveness

The global measures of effectiveness by the clinician (CGI-S and CGI-C) should be completed before the quantitative measure of saliva.

Assessors

In order to maintain consistency of rating assessments, an assessor will be trained (i.e., Investigator or other clinician named on Form FDA 1572) and this same assessor should perform a given assessment for a subject throughout the study. Another assessor (clinician named on Form FDA 1572) will also undergo training to ensure consistency in scale ratings should a back-up assessor be necessary to perform assessment(s).

Caregiver Assistance

If a subject elects to have a caregiver assist with completing rating scale activities, that same caregiver should then consistently assist with the ratings throughout the study. Note that the caregiver may assist in the physical completion of scales, but all responses recorded on the scales must be provided from the subject either verbally or by gesture.

Study Participants with Parkinson's Disease

Therefore, PD subjects should complete the rating scales at least 1 hour after their first dose of PD medication and at least 1 hour postprandial.

Study Participants with ALS

For ALS subjects on short-acting anticholinergics or antihistamines (duration of action of 8 hours or less), for the treatment of troublesome sialorrhea, these medications must be held at least 8 hours before the screening, baseline, and all subsequent study visits, so that the effectiveness of the study drug can be properly evaluated. All subjects must be converted to a short-acting medication (duration of action of approximately 8 hours or less) at least 2 weeks before the first injection of study drug (i.e., Day 1 of Treatment Session 1).

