15.4 Drooling Frequency and Severity Scale (DFSS)

The DFSS will be used to assess the frequency and severity of drooling. The DFSS-I will be performed by a trained assessor independent of the DFSS performed by the subject (DFSS-S) (Appendix E). The DFSS-I will be completed at screening, on Day 1 (i.e., study baseline) before the first injection of study drug, at each subsequent study visit, or, if applicable, at discontinuation from the study. Severity is assessed on a 5-point scale ranging from 1 (dry, never drools) to 5 (profuse, clothing, hands, tray, objects become wet). Frequency is assessed on a 4-point scale ranging from 1 (never drools) to 4 (constantly drools). The DFSS total score ranges from 2 to 9. The assessor’s initial assessment at screening should be based on the prior 4 weeks, with subsequent assessments based on the timeframe since the prior study visit. The assessor should not review the subject-rated scales before performing his/her own assessment. The subject will complete this assessment in the diary on a daily basis for the first 2 weeks of each treatment session and then weekly for the remainder of the treatment session.

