2.9.1 Effectiveness analysis

As subjects receive multiple single-dose injections, each single-dose injection plus its follow-up period will be considered as a treatment session.

Effectiveness measures obtained over each of the treatment sessions include USFR, CGI-S, CGI-C, DFSS-I, DFSS-S, PGI-S, PGI-C, and DIS at the injection visit (i.e., Day 1, except for CGI-C and PGI-C, and Weeks 13, 26, and 39), 4 weeks post-injection (i.e., Weeks 4, 17, 30, and 43), 8 weeks post-injection (i.e., Week 8, first treatment session only), and 13 weeks post-injection (i.e., Weeks 13, 26, 39, and 52). The injection visit of Day 1 and Weeks 13, 26, and 39 is considered the baseline (or pre-injection), respectively, for each of the consecutive treatment sessions 1 through 4.

For each treatment session, effectiveness analysis of the treatment response will be performed on USFR change from pre-injection, DFSS-I change from pre-injection, and DFSS-S change from pre-injection, CGI-S, CGI-C, PGI-S, PGI-C, and DIS change from pre-injection, at each of the post-injection time points using a t-test.

In addition, the proportion of treatment responders will be reported for the CGI-C and PGI-C at both pre-injection and post-injection time points over each treatment session. Before the analysis, the CGI-C and PGI-C will be dichotomized into 2 categories, with "very much improved" and "much improved" into 1 category and the remaining levels in the other category.

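### The 8-hour hold on ALS subjects' sialorrhea medication cannot protect DFSS-I, DIS or the DFSS-S diary, and the SAP does not address on-study changes in that medication

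*Protocol*

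**What the plan says.** Exclusion criterion 9 (Protocol Synopsis and Section 11.1.2) rules out antihistamine and anticholinergic treatment of sialorrhea, with an exception for ALS subjects, for whom "such medications for the treatment of sialorrhea are allowed". A short-acting product "is required at a stable dose/regimen at least 2 weeks before the first injection of study drug", and the subject must "hold the medication for at least 8 hours before the screening, baseline, and all subsequent study visits, so that the effectiveness and safety of" MYOBLOC may be assessed. Section 15 repeats the rule ("these medications must be held at least 8 hours before the screening, baseline, and all subsequent study visits") and gives the reason: "so that the effectiveness of the study drug can be properly evaluated". Section 16.10 again ties the stable regimen to the period before the first injection. No section sets a condition on the regimen after Day 1, and none expressly permits changes.

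The same drug classes taken for another condition, in any diagnosis, are discouraged but allowed, with neither a hold nor a stability condition (criterion 9 and Section 16.10).

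Protocol 15.4 has the DFSS-I completed "with subsequent assessments based on the timeframe since the prior study visit", and 15.5 words the DIS the same way. Footnote (l) of Protocol Table 2 describes the DFSS-S as "Subject-rated via entry in diary (not during study visit), daily for first 2 weeks after study drug injection and then weekly".

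In SAP 2.9.1, "effectiveness analysis of the treatment response will be performed on USFR change from pre-injection"; the other scales are handled alike, by t-test at each post-injection time point. SAP 2.9 puts all subjects in one table group. Concomitant medications are counted by session and listed (SAP 2.9.3 and 5.14). No effectiveness table, covariate or repeat analysis refers to them.

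**The concern.** The hold is the plan's only stated safeguard for reading effectiveness in ALS subjects who keep another antisialorrhea drug. It works where the measurement is a snapshot at the visit. A scale that sums up several weeks at home reflects those weeks, including any effect of the other drug.

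There is no control arm to absorb a change in co-medication, so the effectiveness evidence is change from pre-injection. If a subject takes more of the other drug after Day 1, for example as ALS progresses, the improvement is credited to MYOBLOC. If a subject cuts back because MYOBLOC works, part of the benefit disappears. In the same subject USFR is measured after the hold while DFSS-I, DIS and DFSS-S are not, so the measures may disagree for reasons unrelated to MYOBLOC. The secondary objective is at stake; the primary safety objective is not.

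**Working it through.** The plan gives no figure to reproduce: SAP 2.5 says that no sample size estimation was done, and neither document sizes the effect of this co-medication.

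**Step 1. Which measures can the hold protect?** Time references come from Protocol 15.1 to 15.5 and Table 2.

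| Measure | Period rated | Covered by the hold? |
|---|---|---|
| USFR | 5-minute collection at the visit | Yes |
| CGI-S, PGI-S | Rated at the visit, no recall period stated | Unclear, possibly |
| CGI-C, PGI-C | Change since the session's pre-injection point (PGI-C: since Day 1 or the latest injection) | Unclear |
| DFSS-I | Time since the prior visit | No |
| DIS | 4 weeks at Day 1, then time since the prior visit | No |
| DFSS-S | Home diary | No |

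On explicit text, 3 of 8 measures fall outside the hold. Adding CGI-C and PGI-C because they span the weeks since injection would give 5 of 8.

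**Step 2. How much of a look-back does the hold reach?** Share = 8 h / (weeks × 168 h).

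- 4 weeks (e.g. Day 1 to Week 4): 8/672 = 1.2%
- 5 weeks (Week 8 to 13): 8/840 = 0.95%
- 9 weeks (Weeks 17 to 26, 30 to 39, 43 to 52): 8/1512 = 0.53%

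This is the share of the rated period that the hold secures. It is not an estimate of time under the other drug, because dosing frequency is not given.

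**Step 3. Baseline.** The Day 1 DIS looks back 28 days and stability is required for 14. In a subject who converts at the latest permitted time, 28 − 14 = 14 of 28 baseline days (50%) precede conversion. SAP 2.6.1 gives the Day 1 DFSS-I the same 4-week look-back. Protocol 15.4 places that look-back at screening instead; on that reading the Day 1 DFSS-I covers the time since screening, at most 21 days, of which up to 21 − 14 = 7 may precede conversion. The direction of the resulting error is unknown.

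**Step 4. When does the other drug bias a change score?** As an additive approximation, observed change = MYOBLOC effect + (other-drug effect after − other-drug effect before). Constant use makes the bracket roughly zero. A change in regimen, or a baseline window straddling conversion, does not.

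**Step 5. Size in the pooled mean.** Shift = f × c × d, where f is the share of analysed subjects who are ALS users, c the share of them whose regimen changes, and d the scale points moved in each. None of these is in the documents. Assumed ranges: f = 5% to 30% (9 to 56 of the 187 in SAP 2.5), c = 25% to 100%, d = 0.5 to 2.

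- Lowest: 0.05 × 0.25 × 0.5 = 0.006 points
- Middle: 0.10 × 0.50 × 1 = 0.05 points
- Highest: 0.30 × 1.00 × 2 = 0.6 points

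The formula moves every change the same way; opposing changes partly cancel. In subjects whose regimen changes, the shift is the full d.

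**The case against.** Several stronger conclusions are tempting, and the documents do not support them.

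- **That the hold protects USFR alone, or fails for most measures.** CGI-S and PGI-S have no stated recall period and are rated at the held visit, and PGI-C runs up to the moment of assessment. The scale forms are in appendices not available here. Three of eight measures are clearly outside the hold; more cannot be shown.
- **That about 99% of the rated time is on the other drug.** This does not follow from Step 2. The permitted drug acts for roughly 8 hours or less, and once-daily or as-needed use would leave much of the period uncovered.
- **That stable use distorts the result by lowering the baseline.** A constant regimen is present before and after injection and largely cancels. Subjects also needed a DFSS-I of at least 4 at screening.

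There are also partial controls. Sialorrhea use of these drugs is prohibited outside ALS. Subjects are told to contact staff about any new medication (Section 14.2). A subject needing a prohibited drug may be discontinued (Section 12.3). Medications are reviewed at post-injection visits and most scheduled calls, and deviations are summarised (SAP 3.7). These make changes visible, but they do not carry them into the effectiveness analysis.

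A last objection bears on the remedy. Dropping visits after a drug change conditions on a post-treatment event: subjects may cut back because MYOBLOC works or increase because ALS progresses, so exclusion could introduce selection bias. That stands, and the fix avoids it.

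**Conclusion.** The point holds in limited form. For DFSS-I, DIS and the DFSS-S diary, the hold cannot do what the protocol says it is for. For the CGI and PGI scales its effect cannot be settled from the documents; for USFR it works. The stability rule leaves up to half of the Day 1 DIS look-back exposed in subjects who convert late, and on-study changes in the permitted drug have no place in SAP 2.9.1 or 4.4.

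The bias can go either way and its size is unknown. The pooled range of 0.006 to 0.6 points rests wholly on assumed inputs. Its top end needs 30% users, all changing in the same direction by 2 points; middle values give 0.05 on the DFSS's 2 to 9 range. A small pooled effect is the likelier outcome, with larger distortion confined to subjects whose regimen changed. This is a cheap improvement to a secondary analysis and does not threaten the study's main purpose.

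**What to change.** 1. State in Protocol Section 15 and SAP 2.6.1 that the hold does not cover DFSS-I, DIS or DFSS-S.
2. In SAP 2.9.1 and 4.4, repeat the DFSS-I, DFSS-S, DIS, CGI and PGI summaries without ALS subjects who were on a permitted antisialorrhea drug at Day 1. Show those subjects separately, with USFR as their main measure. The group is fixed at baseline, so treatment response cannot affect who is in it.
3. Describe on-study starts, stops and, if recorded, dose changes of anticholinergics or antihistamines by session, in all diagnoses. Do not exclude the visits that follow. The documents mention new medications and start dates; whether dose-change dates are captured should be confirmed.

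The cost is wording plus one extra set of tables from medication records that are already planned. The repeat tables lose some precision: taking 187 subjects and an unchanged SD, removing 9 (5%) widens confidence intervals by √(187/178) − 1 = 2%, removing 19 (10%) by √(187/168) − 1 = 6%, and removing 56 (30%) by √(187/131) − 1 = 19%. The separate ALS-user table will be small and imprecise and should be read descriptively. No change to the medication rule or to the length of the hold is proposed.
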